### **5.8.1. Non Pharmacologic Interventions**

Subjects participating in this trial may continue all non-pharmacologic therapies such as physical therapy, herbal therapy or homeopathic therapy, if they were begun before screening. These therapies should remain on a stable regimen for the duration of the study.

### **5.8.2. Prohibited Medications**

The following list of medications is prohibited during the entire course of the study.

1. Any live (attenuated) vaccine. Vaccinations with live components are prohibited within 4 weeks prior to the first dose of IP, during the study and for 6 weeks after the last study visit.
2. Treatment with other TNF antagonists, B cell depleters, T cell depleters, immunosuppressants (including biologic agents), and tofacitinib.
3. Multiple NSAIDs.
4. DMARDs other than sulfasalazine, hydroxychloroquine and methotrexate.
5. Dose of oral prednisone  $\geq 10$  mg/day (or equivalent) and used as described in exclusion criteria.
6. Intra-articular, intravenous, subcutaneous and intramuscular corticosteroid injections.
7. Long-acting analgesics and long-acting narcotics.
8. Investigational or experimental drugs.

## **6. STUDY PROCEDURES**

### **6.1. Screening**

Screening tests and procedures should not commence until after the informed consent form has been signed for this study. The results of the tests and procedures should be reviewed with the subject at the BL visit. Subject screening should be conducted within 4 weeks and no less than 5 days prior to the BL visit. The screening period may be extended up to 42 days if repeat imaging is required or when tuberculosis prophylactic therapy is started during the screening period. No re-screening is permitted in this study. However, if screening laboratory test results exclude the subject and the investigator is reasonably certain that the results(s) were due to laboratory error; or in the opinion of the investigator the result(s) were flawed by a transient condition, that laboratory test(s) may be repeated once during the screening period for confirmation.

This change in process must be accurately recorded and documented in the subjects file and the test should be repeated in a very timely manner (within 4 days of obtaining the result). The re-test is done under the same subject number (this will not be considered a re-screening).

### **6.1.1. Screening Procedures**

- Informed consent must be read, signed and dated by subject and witnessed by the investigator or designee.
- Record subject demography and medical history. Medical history evaluation includes; general medical history, disease specific medical history, evaluation of background medication and family medical history.
- Review all inclusion/exclusion criteria.
- Record all prior medications including DMARDs, corticosteroids, and NSAID use. All medications taken within 30 days prior to screening should be recorded.
- Physical examination (performed by a physician) evaluating any clinically significant abnormalities within the following body systems: general appearance, skin, head/eyes/ears/nose/throat, heart, lungs, abdomen, lower extremities, neurological, back/spinal, and lymph nodes. Results must be recorded in the subject's source documents and any significant findings must be recoded on the Medical History CRF and/or appropriate AE CRF.
- Measure height in centimeters (cm) and weight in kilograms (kg).
- Vital sign measurements, including pulse rate (after sitting 5 minutes) and blood pressure. A sitting blood pressure (BP) will be obtained by qualified site personnel. If possible, a different arm should be used for the collection of blood samples.
- BASDAI evaluation.
- SADA.
- Chest radiograph and TB testing:
  - Local country guidelines should be followed for appropriate TB screening in the setting of anti-TNF therapy, including a minimum of:
    - A chest radiograph, to be performed at the screening visit and read locally by a qualified reader unless a chest radiograph has been done within 12 weeks before the screening visit and the report is available and included in the subject's source documents. If required by local regulations, a chest x-ray taken within 6 months of the screening visit may be used as long as the report is available and included in the subject's source documents;

- Objective TB testing, such as Quantiferon or PPD depending on what is available and acceptable per local guidelines.
  - Quantiferon must be used unless not available or not accepted per local guidelines;
  - If the PPD tuberculin skin test is performed, the subject must return 48-72 hours post-test for evaluation. A PPD of >5 mm should be considered positive for TB unless local guidelines for testing of immunocompromised subjects are available and different;
  - TB testing with Quantiferon or PPD need not be done during screening if there is documentation of either test being negative within 12 weeks before the screening visit and if this approach is not prohibited by local guidelines;
  - If the subject is known to be Quantiferon positive or PPD positive, the Quantiferon or PPD tuberculin skin test need not be repeated at the screening visit.
- Collect samples for the following laboratory evaluations:
  - Hematology, blood chemistry, HLA-B27, hsCRP and ESR;
  - Routine urinalysis;
  - Hepatitis B and Hepatitis C testing.
- Serum pregnancy test for women of childbearing potential:

For female subjects and male subjects whose partners are of childbearing potential, evaluate childbearing potential and sexual activity. This discussion should include highly effective methods of contraception (see [Section 4.5](#) Life Style Guidelines). This evaluation and discussion must be documented in the subject's source documents.

- Female subjects who, in the opinion of the investigator, are of childbearing potential will be required to have a serum pregnancy test; this includes subjects who are menstruating at the time of the visit and/or who are not sexually active;
- Urine pregnancy test will also be done whenever one menstrual cycle is missed during the study period or when potential pregnancy is otherwise suspected. Pregnancy tests may also be repeated as per request of IRB/ECs or if required by local regulations.

- X-ray of SIJ - Results of historical x-rays that have been obtained within 4 months (12 months in Germany only) prior to screening could be used in lieu of performing screening x-rays. If historical x-rays are used, the original films, or a copy, must be on site and a copy should be sent to the central imaging vendor. Then central reader must be able to determine the presence of and/or degree of sacroiliitis. If the results are considered unevaluable by the central reader, the x-ray must be repeated. If the subject is unable to have a repeat x-ray due to the regulations issued by the German Federation of Radiation Council, the subject would be considered a screen failure.
- MRI Spine and SIJ - MRI evaluation must occur after SIJ x-rays have been obtained and the report from the central imaging vendor has been reviewed by the investigator. MRI should only occur after the subject is found to meet eligibility criteria by evaluation of the SIJ x-ray.
- Adverse Event reporting - serious adverse events must be reported to Pfizer from the time that the subject provides informed consent.

## **6.2. Baseline (Day 1)**

The baseline visit (Day 1) will occur no later than 4 weeks after the screening visit unless treatment for latent TB or repeat imaging is necessary; for which it may be extended to 6 weeks only. It is intended that all procedures for the baseline visit will occur on the same day. All results from the screening visit (including any repeat laboratory tests) must be available and reviewed before the baseline visit. Baseline tests and procedures must be performed before administration of the first dose of IP. However, results of the baseline laboratory tests (with the exception of urine pregnancy test) are not required in advance of dispensing IP. Should the laboratory results subsequently show that the subject does not meet the inclusion/exclusion criteria and this is confirmed upon retest, the subject must be withdrawn from the study at that time.

For women of childbearing potential, both a serum and urine pregnancy test should be performed at the baseline visit, prior to the first injection of the IP. If the serum pregnancy test at baseline subsequently is resulted as positive, the subject **MUST** be withdrawn from the study.

The following tests and procedures will be performed at the Baseline visit.

- Review all inclusion/exclusion criteria.
- Record prior medications including DMARDs, corticosteroids, and NSAID use.
- Urine and serum pregnancy test.
- Vital signs including sitting BP and pulse.
- Record any AEs that occur following the first dose of investigational product.

- Blood chemistry, hematology, hsCRP and ESR (these parameters do not need to be repeated at the baseline visit if they were completed at the screening visit  $\leq 14$  days before baseline).
- Collect blood samples for banked biospecimens Prep D1, Prep R1 and Prep B1.
- Confirm and document that subject is using highly effective method of birth control.
- Joint assessment 44 count, including MASES (enthesitis) and dactylitis evaluation.
- Assessment of IBD, psoriasis and uveitis.
- BASDAI, BASFI, BAS-G.
- PGA.
- SADA.
- Subject Nocturnal and Total Back Pain Assessment.
- Health Outcomes: EQ-5D, SF-36 and WPAI.
- Open label treatment assignment (first dose).
- Dispense IP and IP diary card if randomized. **The first dose of IP must be administered in the investigational site office by study personnel after all baseline evaluations are completed.**

### 6.3. Induction Period (Period 1)

The following information/assessments will be collected at the study visits for Weeks 4, 8, 12, and 16 (within  $\pm 4$  days of the projected visit date based on the actual baseline visit date); and Week 24 ( $\pm 7$  days of the projected visit date based on the actual baseline visit date). It is intended that all procedures for a visit will occur on the same day. If the Week 24 ASDAS CRP is  $\geq 1.3$ , the subject should be notified by phone that their participation in the study is complete. A follow-up call will be conducted in place of the Week 28 visit to assess new and ongoing adverse events and medication taken to treat them since the last dose of investigational product.

- Review concomitant medications including NSAIDs, DMARDs, and corticosteroids at every visit.
- Vital signs including sitting BP and pulse at every visit.
- Physical examination (performed by a physician) at Week 24.
- Measure height (cm) and weight (kg) at Week 24.

- Review of any AEs at every visit that occurred since the previous visit.
- Collect samples for the following laboratory evaluations:
  - Hematology and blood chemistry at Week 12 and Week 24;
  - hsCRP and ESR at every visit;
  - Urine pregnancy test at every visit;
  - Banked biospecimens Prep B1 and R1 at Week 12 and Week 24.
- Confirm and document at every visit the subject is using a highly effective method of birth control.
- MRI of spine and SIJ at Week 24.
- Joint assessment including MASES (enthesitis) and dactylitis evaluation at Week 12 and Week 24.
- Assessment of IBD, psoriasis and uveitis at every visit.
- BASDAI, BASFI, PGA, SADA, Subject Nocturnal and Total Back Pain Assessment and WPAI at every visit.
- BAS-G, EQ-5D and SF-36 at Weeks 12 and 24.
- Dispense IP and IP diary card at Weeks 4, 8, 12 and 16.
- Collect and review IP diary card at every visit.
- Collect IP and complete IP return and accountability document at every visit.

#### **6.4. Withdrawal Period (Period 2)**

Subjects who are eligible to enter the withdrawal period will have the following assessments performed at all visits during the withdrawal period unless otherwise indicated:

- Review Period 2 eligibility criteria at Week 28.
- Review concomitant medications including NSAIDs, DMARDs, and corticosteroids at every visit.
- Vital signs including sitting BP and pulse at every visit.
- Physical examination (performed by a physician) at Week 64.
- Measure height (cm) and weight (kg) at Week 64.

- Review of any AEs at every visit that occurred since the previous visit.
- Collect samples for the following laboratory evaluations:
  - Hematology, blood chemistry and urinalysis at Week 64;
  - hsCRP and ESR at every visit;
  - Urine pregnancy test at every visit.
- Confirm and document at every visit the subject is using a highly effective method of birth control.
- MRI of spine and SIJ at Weeks 48 and 64.
- Joint assessment including MASES (enthesitis) and dactylitis evaluation at Weeks 32, 48 and 64.
- Assessment of IBD, psoriasis and uveitis at every visit.
- BASDAI, BASFI, PGA, SA DA, Subject Nocturnal and Total Back Pain Assessment and WPAI at every visit.
- BAS-G, EQ-5D and SF-36 at Weeks 32, 48 and 64.

### **6.5. Re-Treatment Period for Subjects in the Withdrawal Phase (Period 3)**

Subjects in the withdrawal period (Period 2) who experience disease flare will be seen for a re-treatment assessment visit at the study site, which should occur as soon as possible after disease flare. The first visit of the Retreatment period (Period 3) may occur at the same time as a regularly scheduled visit during Period 2 or it may occur as an unscheduled visit. Subjects requiring re-treatment (based on a protocol-defined flare of ASDAS ESR greater than or equal to 2.1) will be offered the option to enter re-treatment (Period 3) and receive 12 weekly doses of open-label ETN (50 mg).

Subjects who discontinue (eg, for an adverse event) at any time are ineligible to enter the re-treatment phase.

Subjects who are eligible to enter the re-treatment period will have the following assessments performed at all visits during the re-treatment period unless otherwise indicated:

- Review concomitant medications including NSAIDs, DMARDs, and corticosteroids at every visit.
- Vital signs including sitting BP and pulse at every visit.
- Physical examination (performed by a physician) at Week R12.

- Measure height (cm) and weight (kg) at Week R12.
- Review of any AEs at every visit that occurred since the previous visit.
- Collect samples for the following laboratory evaluations:
  - Hematology and blood chemistry at Weeks R0 and R12;
  - hsCRP and ESR at every visit;
  - Urine pregnancy test at every visit.
- Confirm and document at every visit the subject is using a highly effective method of birth control.
- MRI of spine and SIJ at Weeks R0 and R12.
- Joint assessment including MASES (enthesitis) and dactylitis evaluation at Weeks R0 and R12.
- Assessment of IBD, psoriasis and uveitis at every visit.
- BASDAI, BASFI, PGA, SA DA, Subject Nocturnal and Total Back Pain Assessment and WPAI at every visit.
- BAS-G, EQ-5D and SF-36 at Weeks R0 and R12.
- Dispense IP and IP diary card at Weeks R0, R4, and R8.
- Collect and review IP diary at Weeks R4, R8, R12.
- Collect IP and complete IP return and accountability document at Weeks R4, R8 and R12.

## 6.6. Follow-up Call

A safety follow-up telephone call approximately 28 days after the last dose of investigational product will only be completed for subjects who:

- Receive IP in Period 1, but who do not enter Period 2, or,
- Enter Period 2 and discontinue from the study *before* the Week 28 visit or,
- Enter Period 3 (Retreatment period).

No follow-up is needed if subjects enter Period 2 and do not experience a flare. If required by local regulations, the follow-up visit may be conducted at the study site. It is intended

that all procedures for the follow-up visit will occur on the same day. The following information will be collected:

- Record AEs that were ongoing at the time of the last visit as well as those starting between the last visit and the follow-up call.
- Record medications taken to treat any new or ongoing AEs/SAEs that occurred since the last visit.

### **6.7. Early Discontinuation Visit**

For all subjects who withdraw from the study prior to completing the last visit of any period, the following information/assessments will be collected at the early discontinuation visit. The early withdrawal visit should be completed as soon as possible after the last dose of investigational product. It is intended that all procedures for the early discontinuation visit will occur on the same day.

- Review concomitant medications including NSAIDs, DMARDs, and corticosteroids.
- Vital signs including sitting BP and pulse.
- Physical examination (performed by a physician).
- Measure height (cm) and weight (kg).
- Review of any AEs that occurred since the previous visit.
- Collect samples for the following laboratory evaluations:
  - Hematology and blood chemistry;
  - hsCRP and ESR;
  - Urine pregnancy test;
  - Banked biospecimens Prep B1 and R1 only if subject discontinues during Period 1.
- Confirm and document the subject is using a highly effective method of birth control.
- MRI of spine and SIJ.
- Joint assessment including MASES (enthesitis) and dactylitis evaluation.
- Assessment of IBD, psoriasis and uveitis.

- BASDAI, BASFI, BAS-G, PGA, SADA, Subject Nocturnal and Total Back Pain Assessment, EQ-5D, SF-36 and WPAI.
- Collect and review IP diary card.
- Collect IP and complete IP return and accountability document.

### **6.8. Subject Withdrawal**

The sponsor's Clinical team must be consulted as soon as possible if any of the following occur during the active treatment period (Period 1 or Period 3) to determine whether the subject should continue taking the investigational product:

- Any infection requiring parenteral (IV, IM) anti-infective agents but not meeting criteria for serious infection (see below).
- The sponsor's Clinical team must be notified as soon as possible if a subject is planning to undergo or has undergone any surgical procedure. It is recommended that investigational product be withheld surrounding most surgical procedures.
  - For most planned surgeries, investigational product should be withheld for a period of time prior to the procedure; the specific duration should be determined by the clinical judgment of the investigator;
  - Investigational product should be withheld following most surgeries. The investigational product can be reintroduced once the investigator judges the risk for post-operative infection to be low;
  - If it is clinically judged that more than two consecutive weekly doses of investigational product should be withheld, then the subject must be withdrawn from the study.
- Lack of compliance with the protocol, including protocol required schedule of study visits and/or lack of procedures.

Subjects **MUST** be withdrawn from investigational product if any of the following occurs:

- If baseline lab value is confirmed to meet Exclusion criteria, the subject must be discontinued. Confirmation of the value should be performed prior to the Week 4 visit.
- Pregnancy.
- Grade 3 or 4 systemic toxicity or a SAE thought to be related to investigational product and not alleviated by symptomatic treatment after cessation of investigational product use of up to two doses or Grade 3 or 4 systemic toxicity that recurs after resumption of investigational product use (see [Appendix 5](#)).

- Receipt of any live (attenuated) vaccines.
- Subjects with clinical signs and symptoms suggestive of active tuberculosis should have investigational product withheld until a diagnosis can be confirmed. If diagnosis or tuberculosis is confirmed, investigational product must be discontinued.
- Suspected sepsis.
- Any serious infection (defined as an infection meeting any SAE criteria).
- Confirmed blood dyscrasia or a demyelinating disorder (such as multiple sclerosis or optic neuritis).
- Confirmed malignancy other than squamous cell, basal cell carcinoma or cervical carcinoma in situ.
- If more than 2 consecutive doses of investigational product are missed.
- Joint surgical procedures (open or arthroscopic) and synoviorthesis in Period 1 or Period 3.
- Withdrawal of consent: Subjects who request to discontinue study treatment will remain in the study and must continue to be followed for protocol specified follow-up procedures. The only exception to this is when a subject specifically withdraws consent for any further contact with him or her or persons previously authorized by the subject to provide this information. Subjects should notify the investigator in writing of the decision to withdraw consent from future follow-up, whenever possible. The withdrawal of consent should be explained in detail in the medical records by the investigator, as to whether the withdrawal is only from further receipt of investigational product or also from study procedures and/or post treatment study follow-up, and entered on the appropriate CRF page. In the event that vital status (whether the subject is alive or dead) is being measured, publicly available information should be used to determine vital status only as appropriately directed in accordance with local law.
- Lost to follow-up: All reasonable efforts must be made to locate subjects to determine and report their ongoing status. This includes follow-up with persons authorized by the subject as noted above. Lost to follow-up is defined by the inability to reach the subject after a minimum of 2 documented phone calls, faxes, or e-mails as well as lack of response by the subject to 1 registered mail letter. All attempts should be documented in the subject's medical records. If it is determined that the subject has died, the site will use permissible local methods to obtain the date and cause of death. If the investigator's use of a third-party representative to assist in the follow-up portion of the study has been included in the subject's informed consent, then the investigator may use a sponsor-retained third-party representative to assist site staff with obtaining the subject's contact information or other public vital status data

necessary to complete the follow-up portion of the study. The site staff and representative will consult publicly available sources, such as public health registries and databases, in order to obtain updated contact information. If, after all attempts, the subject remains lost to follow-up, then the last-known-alive date as determined by the investigator should be reported and documented in the subject's medical records.

- Principal investigator decision [ie the investigator or the family doctor considers treatment indicated using a medication that is not permitted (within the scope of the trial)].
- Sponsor decision.
- The study is stopped by the IRB or EC, or by a regulatory agency.

Subjects may withdraw from the study at any time at their own request, or they may be withdrawn at any time at the discretion of the investigator or sponsor for safety or behavioral reasons, or the inability of the subject to comply with the protocol-required schedule of study visits or procedures at a given study site.

If a subject does not return for a scheduled visit, every effort should be made to contact the subject. The number and types of attempts to reach the subject must be documented in the subject's source documents. In any circumstance, every effort should be made to document subject outcome, if possible. The investigator should inquire about the reason for withdrawal, request that the subject return all used/unused investigational product(s) and packages, request that the subject return for a final visit, if applicable, and follow up with the subject regarding any unresolved AEs.

If the subject withdraws from the study, and also withdraws consent for disclosure of future information, no further evaluations should be performed, and no additional data should be collected. The sponsor may retain and continue to use any data collected before such withdrawal of consent.

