- Diagnosis of multiple sclerosis or other central or peripheral nervous system demyelinating diseases;

- Presence or history of cancer (or carcinoma in situ) other than resected cutaneous basal cell or squamous cell carcinoma;
- Uncontrolled diabetes mellitus;
- Diagnosis of rheumatoid arthritis, systemic lupus erythematosus, scleroderma, or polymyositis;
- Open cutaneous ulcers;
- Liver cirrhosis or fibrosis.

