#### **8.14.1. Serious Adverse Event Reporting Requirements**

If an SAE occurs, Pfizer is to be notified within 24 hours of investigator awareness of the event.

In particular, if the SAE is fatal or life-threatening, notification to Pfizer must be made immediately, irrespective of the extent of available AE information. This time frame also applies to additional new information (follow-up) on previously forwarded SAE reports as well as to the initial and follow-up reporting of EDP, exposure via breastfeeding, and occupational exposure cases.

In the rare event that the investigator does not become aware of the occurrence of an SAE immediately (eg, if an outpatient study subject initially seeks treatment elsewhere), the investigator is to report the event within 24 hours after learning of it and document the time of his or her first awareness of the AE.

For all SAEs, the investigator is obligated to pursue and provide information to Pfizer in accordance with the time frames for reporting specified above. In addition, an investigator may be requested by Pfizer to obtain specific additional follow-up information in an

expedited fashion. This information collected for SAEs is more detailed than that captured on the AE CRF. In general, this will include a description of the AE in sufficient detail to allow for a complete medical assessment of the case and independent determination of possible causality. Information on other possible causes of the event, such as concomitant medications, vaccines, and/or illnesses, must be provided. In the case of a subject death, a summary of available autopsy findings must be submitted as soon as possible to Pfizer or its designated representative.

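### The malignancy item on the mandatory-withdrawal list in Protocol section 6.8 exempts squamous cell cancer without limiting it to skin, so read literally this item does not fire for a non-skin squamous cancer

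*Protocol*

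**What the plan says.** Section 6.8 of the Protocol states that subjects must "be withdrawn from investigational product if any of the following occurs". The malignancy entry on that list reads "Confirmed malignancy other than squamous cell, basal cell carcinoma or cervical carcinoma in situ". It puts no limit of site, stage or resection on squamous cell.

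The only other place that says which cancers are tolerated is exclusion criterion 24 in section 4.4: "Presence or history of cancer (or carcinoma in situ) other than resected cutaneous basal cell or squamous cell carcinoma". There the same pair is limited to the skin.

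Section 6.8 also opens with a separate list of events that require consultation with the sponsor's clinical team, during Period 1 or Period 3, on whether dosing should continue. Surgery is on that list: the team "must be notified as soon as possible if a subject is planning to undergo or has undergone any surgical procedure". The SAP does not address the point.

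**The concern.** A mandatory-stop list exists so that sites can act without inferring what was intended. Taken at its word, this item separates cancers by cell type rather than by site. A confirmed adenocarcinoma of the lung stops etanercept at once, while a confirmed squamous carcinoma of the lung falls inside the exemption. The protocol gives no reason for such a difference.

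What is at stake is the safety of an individual subject on a TNF inhibitor. For most cancers the stop is automatic. For a non-skin squamous cancer it would depend on another provision applying, or on someone's judgement.

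**Working it through.** No arithmetic applies. The check sets the two cancer wordings side by side and then asks whether any other provision supplies the missing stop.

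**1. The two wordings.**

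| | Entry (section 4.4, criterion 24) | Stop (section 6.8) |
|---|---|---|
| Squamous and basal cell | exempt only if cutaneous and resected | exempt, no site or resection limit |
| Cervical carcinoma in situ | not exempt | exempt |
| When it applies | at inclusion | on confirmation during treatment |

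The protocol states the skin limit at entry. Nothing carries it into section 6.8, and criterion 24 governs inclusion only. The one item on the stop list that refers back to the exclusion criteria concerns baseline laboratory values.

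**2. Can the grammar rescue the item?** One could read *in situ* across all three terms, so that an invasive squamous cancer would trigger the stop. That is strained, because the word carcinoma is repeated immediately before the cervical term and *in situ* attaches naturally to that term alone. It would also leave non-skin squamous carcinoma in situ exempt.

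**3. Other routes to a stop or review.**

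- *Related serious event.* The list includes "a SAE thought to be related to investigational product and not alleviated by symptomatic treatment" after up to two held doses, together with severe (Grade 3 or 4) systemic toxicity. This needs a judgement of relatedness and a failure to improve, or a recurrence of toxicity when dosing resumes.
- *Missed or withheld doses.* Withdrawal is mandatory when more than 2 consecutive doses are missed or, around surgery, judged to need withholding. With weekly dosing that means at least 3 doses; holding 2 is allowed.
- *Non-permitted medication.* Withdrawal is mandatory if the investigator or family doctor considers a non-permitted medication indicated. Section 5.8.2 bars immunosuppressants, including biologic agents. Section 5.8 item 7 permits medication for conditions not listed among the exclusions, and non-cutaneous cancer is listed there. On the natural reading, drug treatment for such a cancer would therefore trigger withdrawal. The trigger is the indicated drug, not the diagnosis.
- *Surgery.* Consultation with the sponsor on continuing is mandatory, but its outcome is open. The restart sentence reads "The investigational product can be reintroduced once the investigator judges the risk for post-operative infection to be low" and sets no condition about the tumour.
- *Discretion.* Investigator and sponsor decisions are provided for, and subjects can be removed on safety grounds: "they may be withdrawn at any time at the discretion of the investigator or sponsor for safety or behavioral reasons". This permits a stop without requiring one.
- *Serious adverse event reporting.* Under section 8.14.1 the sponsor "is to be notified within 24 hours of investigator awareness of the event". This informs the sponsor but does not stop dosing. Cancer is not itself a seriousness criterion in section 8.6, and section 8.6.1 names no protocol-specified serious events.

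**4. A case that tests the text.** Take a subject in Period 1 with a confirmed squamous cancer of the head and neck, managed by surgery alone, judged unrelated to etanercept, with 2 weekly doses held. The malignancy item does not fire. The related-event, missed-dose and non-permitted-medication items do not fire either. The sponsor must be consulted because of the surgery, and the decision to continue or stop is then a matter of judgement. Had the tumour been an adenocarcinoma, the stop would have been mandatory on confirmation.

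**The case against.** The strongest reply is that this is familiar shorthand and not a wrong rule. Squamous and basal cell named together normally mean skin cancer, and criterion 24 uses the pair in that sense. The item also names the one non-skin site that it means to exempt, the cervix, which suggests that the other two terms were understood as skin. All of this stands as evidence of intent. It does not change what the sentence says, and the reader of a stop list should not have to reconstruct intent.

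Two stronger readings are tempting, and the documents support neither.

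- A reader might infer that a non-skin squamous cancer escapes mandatory withdrawal altogether, or that dosing would continue unreviewed. Only this one item fails to fire. The non-permitted-medication and missed-dose items are themselves mandatory, and planned or completed surgery obliges the sponsor's clinical team to consider whether dosing continues. Most such subjects would be stopped or reviewed.
- A reader might infer that invasive squamous cancer of the cervix is exempt. The item deals with the cervix expressly and exempts it only when in situ. Using the general words to exempt invasive cervical disease would empty that limit.

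**Conclusion.** The point holds in a narrow form. As written, the malignancy item does not fire for a confirmed squamous cancer of a site other than skin or cervix, and no other provision makes the stop automatic on diagnosis. The conclusion rests on a literal reading of one bullet; the intended meaning was very probably skin cancer.

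The practical effect is very small. The documents give no cancer incidence, so no case count can be computed. Subjects are under 50 at consent (section 4.1), and a cancer history other than resected cutaneous lesions is excluded, so few or no cases are to be expected. The residual gap is a subject for whom no non-permitted drug is indicated, no more than 2 consecutive doses are missed or withheld, no unalleviated related serious event or qualifying toxicity occurs, and neither investigator nor sponsor chooses to stop. Sample size, endpoints and analysis are unaffected. This is a correction that the sponsor could make, not one on which the trial depends.

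**What to change.** Reword the bullet in section 6.8 to: *Confirmed malignancy other than cutaneous squamous cell or basal cell carcinoma, or cervical carcinoma in situ.*

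Do not carry over the word resected from criterion 24. The stop rule acts on confirmation, so that word would force withdrawal for a biopsy-confirmed skin lesion still awaiting excision, which the current rule does not require.

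The cost is one added word and a small reordering in a single bullet. It can go into the next protocol amendment, and the SAP needs no change.
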